### 15.2 STUDY ENDPOINTS

#### A. Long-Term Effectiveness (Primary effectiveness endpoint)

The primary effectiveness endpoint is single-procedure freedom from AF/AT recurrence from 3-12 months after the index AF ablation procedure (with 90-day blanking period).

The hypothesis to be tested is the recurrence rate for FIRM-guided AF ablation is not inferior to that experienced by the conventional AF ablation arm.

The statistical hypothesis for this endpoint is operationalized as follows:

$$H_0: \delta > .15$$

$$H_A: \delta < .15$$

$$\alpha = .05 \text{ (two-tailed)}$$

Where:

$$\delta = p_C - p_F$$

$p_C$  = Proportion free from AF recurrence at twelve (12) months post index ablation procedure for the conventional AF ablation arm (.50)

$p_F$  = Proportion free from AF recurrence at twelve (12) months post index ablation procedure for the FIRM-guided AF ablation arm (.55)

The non-inferiority margin for this hypothesis is 15% (.15). If the lower limit of the two-sided 95% confidence interval calculated for the difference in proportions ( $\delta$ ) is less than .15, the null hypothesis will be rejected and evidence in favor of the alternative (FIRM-guided ablation for atrial fibrillation is not inferior to conventional ablation for atrial fibrillation) affirmed.

This non-inferiority margin was chosen based on that used in the FreezeAF and VGLB trials.

 Luik, Armin MD, et. al. (2010). Rationale and design of the FreezeAF trial: A randomized controlled noninferiority trial comparing isolation of the pulmonary veins with the cryoballoon catheter versus open irrigated radiofrequency ablation in patients with paroxysmal atrial fibrillation. American Heart Journal. 159(4):555-560.

The proportion of successes in each treatment arm shall be estimated using Kaplan-Meier survival estimation.

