### 3 BACKGROUND AND RATIONALE

Atrial fibrillation (AF) is the most common sustained arrhythmia in man, and has an increasing population prevalence over time. Treatment is aimed at stroke prevention on the one hand, and amelioration of symptoms (palpitations, lightheadedness, dyspnea, fatigue) due to the arrhythmia. Medical therapy often fails to render a satisfactory response for the latter, prompting the search for alternative therapies. Surgical and, in the last 15 years, catheter ablation techniques have been devised to try to prevent episodes from starting. Groundbreaking work by Haïssaguerre showed that premature discharges or rapid repeated firing from the pulmonary veins (PVs) could trigger AF episodes and that electrical isolation of the PVs could potentially cure the patient of AF. PV isolation currently is a painstaking process consisting of delivering radiofrequency energy or cryoablation in the left atrium to isolate these veins. Such procedures take 2-5 hr. to be completed depending on the complexity of the individual case, and a majority of patients require a 2nd or even 3rd procedure to achieve acceptable antiarrhythmic results. Despite considerable investigative effort, the exact pathophysiology of how PV triggers initiate and or maintain episodes of AF has been elusive.

Recently, a novel mapping technology (RhythmView, Abbott, Menlo Park, CA) based upon the work by Narayan et al has been developed for analyzing atrial recordings during human AF, finding that >95% of cases demonstrate either a rapidly spinning rotor (small circuit) or very rapid focal impulse formation. Furthermore, they have shown that catheter ablation at these relatively circumscribed areas can significantly affect AF, either by substantial slowing of the rate or termination (to an atrial tachycardia or sinus rhythm). In the CONFIRM (CONventional vs Focal Impulse and Rotor Modulation) trial, patients were treated with either conventional mapping and ablation (largely PV isolation or PVI) vs ablation of rotors or sites of focal impulse formation as designated by the mapping algorithm, followed by conventional ablation (PVI). The authors found much higher acute and long-term efficacy when focal impulse and rotor modulation (FIRM procedure) was used (82.4 vs 44% freedom from AF at 24 months post procedure). Although CONFIRM was a controlled study, a randomized evaluation would be warranted.

---

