#### 15.3 POWER AND SAMPLE SIZE ESTIMATION

Since the primary objective of this study relates to the long-term effectiveness of FIRM-guided ablation versus conventional ablation for atrial fibrillation (AF), power and sample size estimates have been calculated relative to that endpoint only. We anticipate enrolling 77 subjects in each treatment arm, plus an additional 8 subjects per arm to account for possible drop-outs / lost to follow-ups, for a total of 170 subjects (in approximately 20 sites).

Description	Assumptions
FIRM Group Freedom from recurrence of AF at 3 months	.55
CONVENTIONAL Group Freedom from recurrence of AF at 3 months	.50
Probability of Type I error ( $\alpha$ ) (two-sided test)	.05
Minimum Total Sample Size (includes 10% adjustment for drop-outs and losses to follow-up)	170 (85 per group)

With 77 subjects in each group, the lower limit of the observed one-sided 95.0% confidence interval will be expected to exceed -0.150 with 80% power when the Standard proportion,  $p_c$ , is 0.500 and the Test expected proportion,  $p_F$ , is 0.550; results are based on 1000 simulations using the Newcombe-Wilson score method to construct the confidence interval. In order to account for potential drop-outs and losses to follow-up, an additional 10% (16) will be added to the total sample size, for a final sample size of 170 (85 per group).

This power and sample size calculation was performed using NQuery 7.0 on the Microsoft Windows 10 operating system.

---

 Newcombe RG (1988) Interval estimation for the difference between independent proportions: comparison of eleven methods. *Statistics in Medicine* 17:873-890.

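### The primary effectiveness rule pre-specifies only a non-inferiority conclusion and tests it on the wrong limit; one rewritten paragraph corrects the limit and adds a superiority step at no extra alpha for this endpoint

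*Protocol*

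**What the plan says.** Protocol 15.2 A, repeated in SAP 2.2.1, tests whether "the recurrence rate for FIRM-guided AF ablation is not inferior to that experienced by the conventional AF ablation arm". It defines delta as pC - pF, so positive values favour PVI, and plans on success proportions of .50 for PVI and .55 for FIRM. On the margin: "The non-inferiority margin for this hypothesis is 15% (.15").

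The decision rule begins "If the lower limit of the two-sided 95% confidence interval calculated for the difference in proportions" and continues that, when this limit is below .15, "the null hypothesis will be rejected and evidence in favor of the alternative" affirmed, meaning that FIRM is not inferior. No other outcome of the interval is given a meaning.

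Nothing elsewhere fills the gap:

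- Protocol 15.2 B to D and SAP 2.2.2 to 2.2.4 state two-sided equality hypotheses for acute effectiveness and both safety endpoints, but not for primary effectiveness.
- The secondary lists (Protocol 6.2 and 15.2 E, SAP 1.2.1.5.2 and 2.3) include single-procedure freedom from recurrence with no hypothesis or test.
- The Cox model in SAP 2.6 is there to examine centre.

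Protocol 15.3 sizes the trial on a different interval and the opposite sign: "the lower limit of the observed one-sided 95.0% confidence interval will be expected to exceed -0.150 with 80% power".

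**The concern.** There are two gaps in the same paragraph.

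First, the objective is to compare effectiveness, the planning values put FIRM ahead, and FIRM is given without the PV ablation that Protocol 3.1 treats as standard of care. A clear difference in either direction would matter to readers. The plan gives neither direction a pre-specified conclusion, although the interval it already computes could support one. A superiority statement first made after the results are known would be post hoc, and operators are not blinded.

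Second, the limit is wrong for the stated sign. With delta = pC - pF, non-inferiority requires the largest plausible deficit, the upper limit, to be below .15. A lower limit below .15 shows only that a deficit beyond the margin has not been proved. Applied as written, the rule could declare FIRM not inferior on data showing it to be worse.

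**Working it through.** **Inputs.** Protocol 15.2 A: margin .15, pC = .50, pF = .55, two-sided 95% interval. Protocol 15.3: 77 evaluable per arm, Newcombe-Wilson interval, one-sided 95% bound, 80% power. Rates of .70, .35 and .30 for FIRM are my assumptions; the documents do not give them.

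**Method.** Wilson limits for each arm: l, u = [2np + z² ∓ z√(z² + 4np(1-p))] / [2(n + z²)]. Newcombe limits for delta = pC - pF:

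- lower = delta - √[(pC - lC)² + (uF - pF)²]
- upper = delta + √[(uC - pC)² + (pF - lF)²]

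Probabilities are sums of the product of the two binomial probabilities over all 78 × 78 = 6,084 possible tables.

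**Step 1: the plan's own figure.** With the one-sided 95% bound (z = 1.645), 77 per arm gives non-inferiority power of 80.6% at .55 against .50. The stated 80% reproduces. With the two-sided 95% interval of the decision rule (z = 1.96), power is 70.7% at 77 and 76.8% at 85 per arm; the sample-size formula at one-sided .025 asks for 98 per arm.

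**Step 2: one table against the rule as written.** Take 39/77 successes on PVI (.5065; Wilson .3972 to .6152) and 26/77 on FIRM (.3377; Wilson .2420 to .4488). Delta = .1688.

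- Lower = .1688 - √(.1093² + .1111²) = .1688 - .1558 = .013
- Upper = .1688 + √(.1087² + .0957²) = .1688 + .1448 = .314

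The whole interval shows FIRM worse, and the upper limit is far beyond .15. But .013 is below .15, so the literal rule affirms non-inferiority.

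**Step 3: how often (77 per arm, two-sided 95%, pC = .50).**

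| True pF | Literal rule affirms non-inferiority | Same, with interval wholly above zero | Upper limit below .15 (correct rule) |
|---|---|---|---|
| .30 | 91.3% | 64.3% | 0.5% |
| .35 (at the margin) | 97.6% | 44.7% | 2.6% |
| .55 | >99.9% | 0.4% | 70.7% |

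**Step 4: alpha for a superiority step.** An upper limit below 0 is necessarily below .15, so superiority can be claimed only where non-inferiority already holds. If the true delta is .15 or more, any false claim is at most the non-inferiority error (2.6% at the margin above). If the true delta lies from 0 to below .15, only the superiority claim can be false; with equal arms its probability is 2.2% at .50 and 2.6% at .40 or .60. Both are close to 2.5% per tail. On the one-sided 95% bound of Protocol 15.3, false superiority at .50 would be about 4.6%.

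**Step 5: what the step would deliver.** Probability that the two-sided interval lies wholly on FIRM's side of zero: 8.3% at .55 against .50; 73.0% at an assumed .70 against .50. Probability that it lies wholly on PVI's side: 73.0% at an assumed .30 against .50. With PVI success near .50, an observed difference of about 16 to 17 points is needed either way.

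**Step 6: can the new outcomes collide?** Non-inferior and less effective can both hold, but in only 2 of the 6,084 tables (0/77 against 5/77, and 72/77 against 77/77, FIRM first). The probability is negligible at rates near .50, but the text should cover it.

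**The case against.** A non-inferiority-only primary hypothesis is an accepted design, and it suits the rationale in Protocol 3.1: PVI is described as slow and damaging to the atrium, so preserving efficacy with a more targeted procedure is a coherent aim. Leaving superiority untested forgoes a claim; it does not bias one. At the plan's own assumptions the step would succeed only about 8% of the time. All of this stands, and it limits the superiority half to a gain in what the trial may claim.

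Three stronger readings are tempting, and the documents do not support them.

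- That a difference could not be concluded at all. The interval would still be computed and can be reported, and the SAP lists a summary table and a Kaplan-Meier figure by group. What is missing is confirmatory status.
- That a poor FIRM result would merely go down as non-inferiority not shown. That describes a correct rule. The written rule would usually affirm non-inferiority.
- That a large advantage is to be expected because "The authors found much higher acute and long-term efficacy when focal impulse and rotor modulation (FIRM procedure) was used". The cited 82.4 against 44% is for FIRM followed by PVI, as freedom from AF at 24 months. This trial gives FIRM without PVI and counts AF/AT from 3 to 12 months.

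The wrong limit may well be a slip. The hypotheses in 15.2 A point the right way, and Protocol 15.3 uses a lower limit above -0.150, which is correct for pF - pC. But the operative rule is the one in 15.2 A, it is repeated unchanged in the SAP, and it should not depend on charitable reading.

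**Conclusion.** The concern holds in two parts. The plan pre-specifies no conclusion beyond non-inferiority, so an interval excluding zero in FIRM's favour would carry only descriptive or post hoc weight. A fixed sequence on the two-sided 95% interval would make it confirmatory with no added alpha. And the written rule uses the wrong limit: at an assumed .30 against .50 it affirms non-inferiority 91% of the time, 64% with the interval wholly above zero.

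The alpha statement has two conditions. It needs the two-sided 95% interval, and it covers this endpoint only: SAP 1.2.1 lists safety among the primary outcomes and SAP 2.7 speaks of multiple primary endpoints without a hierarchy. The probabilities assume complete binary outcomes at 77 per arm and the Newcombe-Wilson interval. The plan estimates the proportions by Kaplan-Meier and does not name the interval method for the analysis, so censoring would shift the figures somewhat.

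It should be corrected before outcomes by arm are examined. The limit is the more serious part; the superiority step is a worthwhile addition.

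**What to change.** Replace the decision rule in Protocol 15.2 A and SAP 2.2.1 with the following, on one two-sided 95% interval for delta = pC - pF:

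1. Upper limit below .15: FIRM is non-inferior.
2. Only if 1 holds, upper limit below 0: FIRM is superior, at the same alpha.
3. Lower limit above 0: reported as FIRM less effective than PVI. If 1 also holds, report both statements.
4. Otherwise: inconclusive.

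In the same amendment:

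- Name the analysis set for the superiority step, preferably all randomized subjects eligible for the procedure. The present ITT set leaves out randomized subjects with no catheter inserted, and SAP 2.5.1 expects some eligibility failures after randomization.
- Name the interval method to be used with the Kaplan-Meier estimates.
- Bring Protocol 15.3 and SAP 2.4 into line with the two-sided 95% interval.
- State superiority power as about 8% at .55 against .50 and about 73% at an assumed .70 against .50, and do not rest the step on 82.4 against 44%.

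The cost is one paragraph in each document plus the alignment of the sample-size text. The superiority step needs no patients, data or alpha. The alignment does bring into view a shortfall that the two-sided rule already carries: 70.7% non-inferiority power at 77 per arm, against 98 per arm for 80%. The sponsor should accept that or address it openly.

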## 2.4 Power and Sample Size Estimation

Since the primary objective of this study relates to the long-term effectiveness of FIRM-guided ablation versus conventional ablation for atrial fibrillation (AF), power and sample size estimates have been calculated relative to that endpoint only. We anticipate enrolling 77 subjects in each treatment arm, plus an additional 8 subjects per arm to account for possible drop-outs / lost to follow-ups, for a total of 170 subjects (in approximately 20 sites).

Description	Assumptions
FIRM Group Freedom from recurrence of AF at 3 months	.55
CONVENTIONAL Group Freedom from recurrence of AF at 3 months	.50
Probability of Type I error (¶) (two-sided test)	.05

Minimum Total Sample Size (includes 10% adjustment for drop-outs and losses to follow-up)	170 (85 per group)
--	--------------------

With 77 subjects in each group, the lower limit of the observed one-sided 95.0% confidence interval will be expected to exceed -0.150 with 80% power when the Standard proportion,  $p_C$ , is 0.500 and the Test expected proportion,  $p_F$ , is 0.550; results are based on 1000 simulations using the Newcombe-Wilson score method to construct the confidence interval. In order to account for potential drop-outs and losses to follow-up, an additional 10% (16) will be added to the total sample size, for a final sample size of 170 (85 per group).

This power and sample size calculation was performed using NQuery 7.0 on the Microsoft Windows 10 operating system.

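### The primary non-inferiority rule tests the wrong confidence limit: read literally, it passes FIRM 97.6% of the time when FIRM is exactly on the 15-point margin

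*Protocol*

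**What the plan says.** Protocol 15.2 A and SAP 2.2.1 carry the same text, apart from the symbol used for the difference. They set:

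- difference = pC − pF, where p is the proportion free from recurrence at 12 months (C conventional, F FIRM);
- H0: difference > .15, and HA: difference < .15;
- "The non-inferiority margin for this hypothesis is 15% (.15"), with alpha .05, two-tailed.

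The decision rule follows: "If the lower limit of the two-sided 95% confidence interval calculated for the difference in proportions" (pC − pF) "is less than .15, the null hypothesis will be rejected and evidence in favor of the alternative". On estimation, the section adds: "The proportion of successes in each treatment arm shall be estimated using Kaplan-Meier survival estimation". It names no interval method for the difference.

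The power sections (Protocol 15.3, SAP 2.4) state a different criterion. With 77 per group, pC = .500 and pF = .550, "the lower limit of the observed one-sided 95.0% confidence interval will be expected to exceed -0.150 with 80% power", using the Newcombe-Wilson score interval. The table in the same sections labels the .05 type I error as a "two-sided test".

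**The concern.** Two things do not fit together.

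1. **Direction.** Because the difference is conventional minus FIRM, evidence for HA is an interval lying wholly below .15, so the upper limit must be below .15. The written rule is met by any interval that merely starts below .15, including a wide one centred well above it. Failing to prove inferiority would count as proving non-inferiority.
2. **Confidence level.** The rule uses a two-sided 95% interval, which is a one-sided test at .025. The power sentence uses a one-sided 95% limit, which is a test at .05. Once the direction is corrected, this choice can itself decide the result, and it determines whether the stated 80% power is true.

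This sentence decides the only endpoint for which the trial is powered. A result whose interval straddles .15 would meet the written rule and fail the hypotheses beside it. Settling that after the data are seen would be a post-hoc change to the primary test.

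**Working it through.** **Inputs.** pC = .50, pF = .55, margin .15, 77 evaluable per arm and the Newcombe-Wilson interval (Protocol 15.3, SAP 2.4); 85 per arm as enrolled. *Assumption:* simple binomial proportions, except in step 5.

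**1. The plan's own power figure.** By normal approximation, SE = √[(.50×.50 + .55×.45)/77] = √(.4975/77) = .0804. The distance from the expected difference (−.05) to the margin (.15) is .20, and .20/.0804 = 2.488.

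- One-sided 95% limit: 2.488 − 1.645 = .843, power 80.0%.
- Two-sided 95% limit: 2.488 − 1.960 = .528, power 70.1%.

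Exact enumeration of all outcome pairs with Newcombe-Wilson limits gives 80.6% and 70.7%. The stated 80% is reproduced, but only with the one-sided 95% limit.

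**2. Direction.** The power criterion, a lower limit above −.150, is a valid test only for pF − pC. Reversing the sign turns it into an upper limit for pC − pF below .15. The hypotheses and the power section therefore agree with each other, and the decision sentence disagrees with both.

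**3. How often each rule declares non-inferiority.** For each pair (xC, xF), compute the two-sided 95% Newcombe-Wilson limits for pC − pF, then sum the binomial probabilities of the pairs that pass (pC = .50).

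| True pC − pF | As written (lower < .15), n = 77 | As written, n = 85 | Upper < .15, n = 77 | Upper < .15, n = 85 |
|---|---|---|---|---|
| .15 (margin) | 97.6% | 97.8% | 2.6% | 2.8% |
| .20 | 91.3% | 91.0% | 0.5% | 0.5% |
| .25 | 76.0% | 73.7% | 0.1% | <0.1% |
| .30 | 49.8% | 45.0% | <0.1% | <0.1% |
| −.05 (plan's assumption) | 100% | 100% | 70.7% | 76.8% |

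Wald limits give 97.2% for the written rule on the margin with 77 per arm. With the one-sided 95% upper limit, the margin figure is 5.0% (n = 77) or 5.4% (n = 85), and power is 80.6% or 85.0%.

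**4. A data set that passes.** Take conventional 38/77 = .4935 (Wilson limits .3848 to .6028) and FIRM 15/77 = .1948 (.1218 to .2969). The difference is .2987.

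- Lower limit: .2987 − √[(.4935 − .3848)² + (.2969 − .1948)²] = .2987 − .1491 = .1496.
- Upper limit: .2987 + √[(.6028 − .4935)² + (.1948 − .1218)²] = .2987 + .1315 = .430.

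The lower limit is just under .15, so the written rule calls FIRM non-inferior although it did 30 points worse.

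**5. Kaplan-Meier check.** The documents estimate the proportions by Kaplan-Meier and censor losses (SAP 2.5), so the rules were also simulated on that basis: 85 per arm, 20,000 trials, Greenwood variance and a Wald 95% interval. *Assumptions:* exponential recurrence over the nine months after blanking, and 10% censored by month 12. The written rule passes 97.1% on the margin and 89.4% at .20. The upper-limit rule passes 2.5% on the margin and has 71.5% power. A repeat of the simulation agreed to within 0.3 percentage points.

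**The case against.** The strongest reply is that this is a slip nobody would act on. The hypotheses and margin stand in the same section, the power text points the right way, and the likely cause is a mix of two sign conventions. On that view 97.6% describes a literal reading, not how the trial would be analysed, and the 38/77 versus 15/77 example was chosen to pass only just. This is fair as to intent, and the figures should be read that way. It does not remove the need for correction: the sentence is the pre-specified rule, it is the same in both documents, and nothing elsewhere overrides it.

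A second reply is that the confidence level is a separate matter on which the documents support either reading: two-sided in the rule, the alpha lines and the power table, but one-sided in the only calculation reported. That also stands. The documents do not settle the choice, so it is the sponsor's to make. The conflict belongs in the same amendment because correcting the limit alone would leave a rule that does not have the stated power.

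Third, the 76.8% power applies only if all 85 per arm are evaluable. The plan allows for 10% loss, so about 71% is the relevant figure, as the Kaplan-Meier check confirms.

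**Conclusion.** The concern holds. As written, the primary decision rule in Protocol 15.2 A and SAP 2.2.1 contradicts the hypotheses it is meant to test and gives no useful control of false non-inferiority claims: about 97 to 98% on the margin, against about 2.5% for the upper limit of the same interval. The margin result hardly depends on the interval method or on 77 versus 85 per arm, because any nominal two-sided 95% interval has its lower limit below the true value about 97.5% of the time. The figures away from the margin assume pC = .50 and binomial or exponential outcomes, as stated in the working.

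The linked conflict also holds: 80% power belongs to a one-sided 95% limit. With the two-sided 95% interval in the rule, power is about 71% at 77 evaluable per arm. Both points must be corrected before the primary comparison is seen.

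**What to change.** **Limit.** In Protocol 15.2 A and SAP 2.2.1, reject H0 if the *upper* limit of the two-sided 95% confidence interval for pC − pF is below .15 (equivalently, if the lower limit for pF − pC is above −.15). Write H0 as difference ≥ .15 so that the boundary belongs to the null. Name the interval method for the Kaplan-Meier difference in the same sentence. This costs only a wording change in each document.

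**Confidence level.** Make the rule agree with Protocol 15.3 and SAP 2.4, in one of two ways:

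- *Preferred:* keep the two-sided 95% interval, which the rule, the alpha lines and the power table already state. Restate power as about 71% with 77 evaluable per arm, and about 77% only if all 85 are evaluable. The cost is a less favourable power statement. For scale, 80% power would need about 95 evaluable per arm by exact enumeration (79.1% at 94, 81.8% at 95) or 98 by normal approximation. Enlarging the trial is optional and is not needed to correct the error.
- *Alternative:* write the one-sided 95% limit into the rule and say openly that the one-sided type I error is .05, not .025. This keeps the 80% power at the price of a weaker standard of evidence.
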